15.3 Analysis of Primary Endpoint

This is a small descriptive study, with the primary tolerability endpoints: 1) peak symptom level and composite score during the treatment period and 2) symptom level and composite score at the end of treatment exposure.

Symptom level over time during the treatment period will be graphed for visualization along the three axes of pain, stinging/burning, and itching/pruritus as well as a composite symptom score. Peak symptom level during the treatment period and pain at the end of treatment exposure will be compared between the conventional treatment arm (A), the combination treatment arm B), and the daylight treatment arm (C), with unpaired t-tests.

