RATIONALE	
Actinic keratoses (AK) are common precancerous skin lesions that arise on sun-damaged skin. Treatment is aimed at preventing progression to cutaneous squamous cell carcinoma (SCC). First-line therapy for clinically apparent lesions includes cryotherapy and curettage; and field therapy options are topical 5-fluorouracil, imiquimod, ingenol mebutate, and photodynamic therapy (PDT). PDT involves the topical application of aminolevulinic acid (ALA), or one of its derivatives, as a photosensitizing agent. In response, rapidly proliferating, dysplastic cells preferentially accumulate protoporphyrin IX (PpIX). When PpIX is activated by blue or red light, singlet oxygen species are produced, resulting in cell death. PDT is beneficial due to its brief treatment course and efficacy in clearing AK. However, its main drawbacks are the adverse effects of pain, burning, pruritus, erythema, crusting, and inflammation associated with treatment. While conventional PDT uses red or blue artificial light to activate a high concentration of accumulated protoporphyrins, daylight PDT uses natural daylight to activate lower levels of protoporphyrins in a continuous manner. Daylight PDT, when compared with conventional PDT, has been associated with significantly less pain while achieving comparable efficacy for the treatment of AK. Daylight PDT is also more cost-effective and reduces the amount of time spent in clinic. Previous randomized studies comparing daylight PDT with conventional PDT have largely used methyl-aminolevulinate as the photosensitizer, have been intra-individual comparative studies, and have been performed in Nordic countries. Because the effective light dose from natural daylight depends on geographic location and seasonal and weather changes, randomized trials in different geographic and environmental conditions are of interest. The proposed randomized clinical trial investigates the tolerability and efficacy of daylight ALA-PDT for the treatment of AK in San Francisco for the first time; subjects will be randomized to various treatment arms, as opposed to previous split-face and intra-individual studies.

STUDY DESIGN	Randomized (1:1:1), single-blind controlled trial with parallel group design
PRIMARY OBJECTIVE	To determine whether daylight PDT affords a reduction in treatment symptoms of pain, burning, and pruritus as measured by 1) symptom level during the treatment period and 2) pain at the end of treatment exposure.

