
TEST PRODUCT, DOSE, AND ROUTE OF ADMINISTRATION
	
Study medication—Aminolevulinic acid HCl topical solution 20% (Levulan Kerastick)
 
Study device—BLU-U blue light phototherapy illuminator
 
After preparation of the treatment area with acetone, one stick of Levulan (containing 354 mg ALA HCl) will be topically applied to the treatment area (face or scalp). Subjects will be randomized to one of three treatment arms to receive BLU-U exposure and/or daylight exposure. Treatment arms are as follows:
 
A. Conventional arm: Acetone preparation, ALA topical application, 1hour incubation, 16 minutes 40 seconds (16:40) BLU-U exposure, application of sunscreen.
 
B. Combination arm: Acetone preparation, ALA topical application, 15 minute incubation, 16:40 BLU-U exposure, application of sunscreen, 45 minute daylight exposure.
 
C. Daylight arm: Acetone preparation, ALA topical application, 15 minute incubation, application of sunscreen, 1 hour daylight exposure.

DURATION OF SUBJECT PARTICIPATION AND DURATION OF STUDY
	
Subjects will be on study for up to 115 days.
 
Screening: up to 30 days
 
Treatment: 1 day
 
Follow-up: 84 days
 
The total duration of the study is expected to be 16 months. Approximately 12 months for subject enrollment and 4 months for treatment and final subject follow-up.

CONCOMITANT MEDICATIONS	Allowed: Bland topical emollients such as Eucerin, Cetaphil. Prohibited: Any topical prescription medication on the treatment area during the study.
EVALUATIONS	
PRIMARY ENDPOINT	Primary objective is to determine whether daylight PDT affords a reduction in treatment symptoms of pain, stinging/burning, and itching/pruritus. Primary endpoints will be: 1) peak symptom level and composite score during the treatment period 2) symptom level and composite score at the end of treatment exposure.
SECONDARY ENDPOINTS	1) To determine efficacy in clearance of AK at 12 weeks: A. percent reduction in number of AKs from baseline to 12 weeks B. proportion of subjects with complete and partial clearance of AKs as described above 2) To determine whether daylight PDT affords, at end of treatment, a reduction in composite local skin reaction 3) To determine whether daylight PDT has a faster resolution of composite treatment symptoms and local skin response during days 8, 29, and 84.

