3 STUDY OBJECTIVES

3.1 Primary Objective

To determine whether daylight PDT affords a reduction in treatment symptoms of pain, stinging/burning, and itching/pruritus.

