5 CRITERIA FOR EVALUATION

5.1 Primary Efficacy Endpoint

The primary efficacy endpoint will be (1) symptom level during the treatment period and (2) pain at the end of treatment exposure.

With these endpoints, we will be able to determine whether daylight PDT offers a reduction in treatment symptoms of pain, burning, and pruritus.

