15.4 Analysis of Secondary Endpoints

Efficacy and tolerability data will be summarized by each secondary endpoint.

Symptom level over time during the treatment period will be graphed for visualization along the three axes of pain, stinging/burning, and itching/pruritus as well as a composite symptom score. Peak symptom level during the treatment period and pain at the end of treatment exposure will be compared between the conventional treatment arm (A), the combination treatment arm B), and the daylight treatment arm (C), with unpaired t-tests.

Percent reduction in the number of actinic keratoses and proportions of patients with partial and complete clearance of actinic keratoses will be presented descriptively and visualized as histograms. We will compare the percent reduction in the number of AKs and the proportions of patients with clearance between the conventional treatment arm (A) and the combination treatment arm B), and between the conventional treatment arm (A) and the daylight treatment arm (C), using unpaired t-tests.

All analyses will be based on the intent-to-treat (ITT) population. In the ITT population, patients will be counted in the treatment group upon randomization, regardless of receiving any dose of study medication. For efficacy analysis, all missing values due to patient early termination from the study will be imputed using last observation carried forward (LOCF) method, as appropriate. For each patient, the Baseline values will be defined as those values recorded at Day 1 prior to dosing. Patients who are lost-to-follow-up after Baseline will be included to the ITT population carrying forward their Baseline values.

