15.6 Sample Size and Randomization

This is a small descriptive study. With ten subjects in each group, we will be powered to detect a 1.25-point difference in pain (pain scale 1-10) with a two-sided alpha of 0.05 and a power of 0.8.

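### The end-of-exposure primary endpoint has two conflicting definitions, and the primary tests name no lead score, arm pair, order or adjustment

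*Combined protocol and SAP*

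**What the plan says.** The end-of-exposure primary endpoint is stated in these places:

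- Synopsis, Primary Objective: "1) symptom level during the treatment period and 2) pain at the end of treatment exposure".
- Section 5.1: "1) symptom level during the treatment period and (2) pain at the end of treatment exposure".
- Synopsis, Primary Endpoint: "2) symptom level and composite score at the end of treatment exposure".
- Section 15.3, opening sentence: "1) peak symptom level and composite score during the treatment period and 2) symptom level and composite score at the end of treatment exposure".
- Section 15.3, test sentence, repeated in the synopsis analysis plan and in 15.4: "Peak symptom level during the treatment period and pain at the end of treatment exposure will be compared", across arms A, B and C with unpaired t-tests.

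Section 9.1.8 provides four scores at each assessment: pain, stinging/burning and itching, each 0-10, and their sum, 0-30. The objective in section 3.1 covers all three symptoms: "To determine whether daylight PDT affords a reduction in treatment symptoms of pain, stinging/burning, and itching/pruritus".

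For the actinic keratosis outcomes, 15.4 does name its pairs: A v B, and "between the conventional treatment arm (A) and the daylight treatment arm (C), using unpaired t-tests". Section 15.6 says "we will be powered to detect a 1.25-point difference in pain (pain scale 1-10"), with two-sided alpha 0.05 and power 0.8. It gives no assessment time and no arm pair. Section 15 calls for a separate SAP before the final data are analysed. No section gives a success rule, testing order or multiplicity adjustment.

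**The concern.** Pain alone is one score. Symptom level plus composite is up to four. These are different endpoints, and both are called primary. End-of-exposure stinging/burning, itching and composite are declared primary in 15.3 and then left out of its test sentence. The other tested quantity, peak symptom level, does not say which symptom, or whether the composite peak is included.

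The authors named pairs for lesion clearance but not for the primary endpoint. Someone following 15.3 as written would run several t-tests at 0.05 and have no rule for which of them answers the primary objective. The SAP that could supply the rule is due only before the final analysis, and section 14 gives the investigator access to all study data. Nothing therefore requires the choice to be made before outcomes are visible.

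**Working it through.** **1. The plan's own figure.** Section 15.6 gives n = 10 per arm, a difference of 1.25 points, two-sided alpha 0.05 and power 0.8, but no SD, so it cannot be reproduced directly. Solving backwards, a two-sample t-test with 10 per arm has power 0.8 at a standardised difference of 1.325, so the implied SD is 1.25 / 1.325 = 0.94. This power belongs to one test of one pain score in one pair. At the same SD, a Bonferroni split over two pairs (0.05 / 2 = 0.025) gives power of about 0.70, and over three pairs (0.05 / 3 = 0.0167) about 0.63.

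**2. The definitions side by side.**

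| Place | During treatment | End of exposure |
|---|---|---|
| Synopsis, Primary Objective | symptom level | pain |
| 5.1 | symptom level | pain |
| Synopsis, Primary Endpoint | peak symptom level and composite | symptom level and composite |
| 15.3, opening sentence | peak symptom level and composite | symptom level and composite |
| 15.3, test sentence (also synopsis analysis plan, 15.4) | peak symptom level | pain |

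The middle column is vague. The right-hand column is contradictory.

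**3. Number of tests in the test sentence, over three pairs (A-B, A-C, B-C).**

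- Peak read as pain: (peak pain + end pain) x 3 = 2 x 3 = 6.
- Peak read as three symptoms plus composite: (4 peaks + end pain) x 3 = 5 x 3 = 15.

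**4. Chance of at least one p<0.05 when the arms do not differ.** This is a simulation with 10 per arm, normal scores, three symptoms at 15, 30, 45, 60 and 75 minutes (9.1.8), peak = largest of the five readings, end = the 75-minute reading, and pooled t-tests at two-sided 0.05. The same correlation is used between symptoms and between times. It is not in the documents and is assumed to lie between 0.3 and 0.8; higher correlation gives the lower rate.

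| Set tested | Tests | False-positive chance |
|---|---|---|
| One score, C v A | 1 | about 5% |
| Peak and end pain, C v A | 2 | about 7-9% |
| Peak and end pain, three pairs | 6 | about 17-21% |
| Four peaks and end pain, three pairs | 15 | about 27-41% |

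Under the opposite rule, where peak and end pain must both be significant for C v A, the rate is only about 1-3%. The plan does not say which rule applies.

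**5. When exposure ends.** The synopsis, 4.1 and 8.4.1 give arm B 45 minutes of daylight. Appendix III labels it 60 minutes, starting at the 30-minute row, yet ends it at the 75-minute row; 30 + 60 = 90, whereas 30 + 45 = 75. The end-of-exposure reading in arm B therefore has no settled time.

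**The case against.** The strongest reply is that the intent is fairly clear. The title compares daylight with conventional treatment, the objective concerns daylight PDT, 15.6 is about pain, and the test sentence uses end-of-exposure pain in all three places where it appears. A reader might infer from the conflict that the primary question is unknowable. The documents do not support that, because they lean towards C v A and pain. What stands is that no section says so.

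The plan also calls itself small and descriptive, in 15.3 among other places, and makes no confirmatory claim. This softens the multiplicity point. It does not remove it, since the plan also states primary endpoints, t-tests, an alpha and a power. Nor does it touch the contradiction: a descriptive study also needs one definition of its primary endpoint.

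Two other counts are tempting. Testing every declared score over three pairs gives 4 x 2 x 3 = 24 tests, but the test sentence does not plan them. Reading peak as pain and keeping only A-B and A-C gives 2 x 2 = 4, but that borrows its pairs from the lesion-clearance sentence. Neither is what 15.3 writes.

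Finally, a reader might infer that the endpoint will be chosen after results are seen. The documents show only that this is not prevented. A SAP is promised before the final analysis, and 15.5 plans no interim analysis.

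**Conclusion.** The concern holds as a contradiction in the text joined to an incomplete testing rule. The end-of-exposure primary endpoint is defined in two incompatible ways, 15.3 contains both, and several unadjusted tests at 0.05 follow from its test sentence. This should be corrected.

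The error rates are illustrative. They assume that any single significant result would count as success, which the plan does not say, and they rest on assumed correlations and normal scores. With correlations of 0.9, under a simpler model, the 15-test figure falls to about 22%. If the reader takes the hint of C v A and pain, what remains is about 7-9%, so the large figures should not be read as the trial's actual error rate. The contradiction itself depends on none of these assumptions.

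**What to change.** Before any outcome data are seen:

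- Use one primary endpoint definition in the synopsis, 3.1, 5.1 and 15.3. Name one pain score, either peak pain over the 15-75 minute assessments or pain at the end of exposure. Pain fits the existing power statement; the sponsor chooses which score.
- In 15.3, make C v A on that score the primary comparison at two-sided 0.05. Test B v A on the same score at 0.05 only if C v A is significant; otherwise report a mean difference with 95% CI. This fixed order keeps the error over both comparisons at 5% without the power loss of a Bonferroni split.
- Make all other symptom and composite scores, and B v C, secondary, reported as mean differences with 95% CIs and no significance claims.
- In 3.1, state that pain is primary and that stinging/burning, itching and the composite are supportive.
- In 15.6, name the same score and pair.
- Delete the repeated primary test sentence from 15.4.
- If end-of-exposure pain is chosen, reconcile the arm B daylight durations in the synopsis, 4.1 and 8.4.1 with Appendix III, so that the assessment time is defined.

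The statistical changes are to wording only; sample size, visits and data collected stay as they are. The price is that the other scores lose primary status, and B v A gets no formal test if C v A is not significant.

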2 STUDY RATIONALE

Actinic keratoses (AK) are common precancerous skin lesions that arise on sun-damaged skin. Treatment is aimed at preventing progression to cutaneous squamous cell carcinoma (SCC). First-line therapy for clinically apparent lesions includes cryotherapy and curettage; and field therapy options are topical 5-fluorouracil, imiquimod, ingenol mebutate, and photodynamic therapy (PDT). PDT involves the topical application of aminolevulinic acid (ALA), or one of its derivatives, as a photosensitizing agent. In response, rapidly proliferating, dysplastic cells preferentially accumulate protoporphyrin IX (PpIX). When PpIX is activated by blue or red light, singlet oxygen species are produced, resulting in cell death. PDT is beneficial due to its brief treatment course and efficacy in clearing AK. However, its main drawbacks are the adverse effects of pain, burning, pruritus, erythema, crusting, and inflammation associated with treatment. While conventional PDT uses red or blue artificial light to activate a high concentration of accumulated protoporphyrins, daylight PDT uses natural daylight to activate lower levels of protoporphyrins in a continuous manner. Daylight PDT, when compared with conventional PDT, has been associated with significantly less pain while achieving comparable efficacy for the treatment of AK. Daylight PDT is also more cost-effective and reduces the amount of time spent in clinic. Previous randomized studies comparing daylight PDT with conventional PDT have largely used methyl-aminolevulinate as the photosensitizer, have been intra-individual comparative studies, and have been performed

in Nordic countries. Because the effective light dose from natural daylight depends on geographic location and seasonal and weather changes, randomized trials in different geographic and environmental conditions are of interest. The proposed randomized clinical trial investigates the tolerability and efficacy of daylight ALA-PDT for the treatment of AK in San Francisco for the first time; subjects will be randomized to various treatment arms, as opposed to previous split-face and intra-individual studies.

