4 STUDY DESIGN

4.1 Study Overview

This is a randomized (1:1:1) controlled trial with parallel group design. Thirty adult subjects are planned; with 10 subjects in each of three treatment arms.

Screening data will be reviewed to determine subject eligibility. Subjects who meet all inclusion criteria and none of the exclusion criteria will be entered into the study.

The following medications and devices will be used:

- (1) Aminolevulinic acid HCl topical solution 20% (Levulan Kerastick)
- (2) BLU-U blue light phototherapy illuminator

Three treatment arms to be compared are as follows:

- A. Conventional arm:** Acetone preparation, ALA topical application, 1 hour incubation, 16:40 BLU-U exposure, application of sunscreen.
- B. Combination arm:** Acetone preparation, ALA topical application, 15 minute incubation, 16:40 BLU-U exposure, application of sunscreen, 45 minute daylight exposure.
- C. Daylight arm:** Acetone preparation, ALA topical application, 15 minute incubation, application of sunscreen, 1 hour daylight exposure.

Total duration of subject participation will be up to 115 days. Total duration of the study is expected to be 16 months.

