6.2 Inclusion Criteria

- Adults at least 18 years old.
- Subjects must be able to read, sign, and understand the informed consent
- Subjects have at least 4 and no more than 20 clinically typical, visible actinic keratoses in the target treatment area on the face or scalp.
- Subject must be willing to forego any other treatments for AK in the treatment area on the face or scalp, during the study period, and for 14 days prior to enrollment; including cryotherapy, topical 5-fluorouracil, imiquimod, and ingenol mebutate.
- Subjects who have previously received PDT must undergo at least an 8-week washout period prior to enrollment in study.
- Subject must be willing and able to participate in the study and to comply with all study requirements including concomitant medication and other treatment restrictions, and telephone interview.
- If subject is a female of childbearing potential she must have a negative urine pregnancy test result prior to study treatment initiation and must agree to use an approved method of birth control while enrolled in the study. Women who are pregnant, lactating, or planning to become pregnant during the study period are excluded from the study.

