9.1.6 Actinic keratosis (AK) count

An AK count will be performed to count the lesions in the treatment area. AK count will be performed at Screening and at days 1, 8, 29, and 84.

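### Primary symptom comparisons are valid but unadjusted; one three-arm model with the Day 1 pre-ALA AK count would be a cheap, conditional efficiency gain

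*Combined protocol and SAP*

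**What the plan says.** Section 15.3 names the primary tolerability endpoints as "1) peak symptom level and composite score during the treatment period and 2) symptom level and composite score at the end of treatment exposure". It says that peak symptom level and end-of-exposure pain "will be compared between the conventional treatment arm (A), the combination treatment arm B), and the daylight treatment arm (C), with unpaired t-tests". The synopsis and section 15.4 repeat this, and none of the three names a covariate.

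On lesion load, section 6.2 admits subjects with "at least 4 and no more than 20 clinically typical, visible actinic keratoses in the target treatment area". Section 9.1.6 states: "AK count will be performed at Screening and at days 1, 8, 29, and 84". In section 10.2 the blinded investigator counts lesions at step 5, before curettage (step 7) and ALA (step 8). Section 15.4 defines baseline as the Day 1 value before dosing.

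The symptom scores in section 9.1.8 start 15 minutes after application, and Appendix I lists none at Screening, so there is no pre-treatment symptom score. Sections 8.1 and 10.2 describe randomization without stratification on AK count. Section 15.2 does not list AK count among the baseline summaries.

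On size, section 4.1 says: "Thirty adult subjects are planned; with 10 subjects in each of three treatment arms". Section 15.6 claims power for a 1.25-point pain difference "with a two-sided alpha of 0.05 and a power of 0.8", and gives no SD.

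**The concern.** With 10 subjects per arm the trial has little precision to spare. If lesion load is related to treatment symptoms, an unadjusted test leaves that variation in the error term, and a chance difference in load between arms passes into the estimated arm difference. The usual remedy, adjusting for the baseline value of the outcome, is not available because that value is not collected. The Day 1 AK count is the obvious pre-treatment measure of disease load, and it is already scheduled. Choosing to adjust only after seeing an imbalance would not be credible, so the decision belongs in the plan. The stake is some power and a narrower confidence interval for the tolerability comparison. It concerns the primary symptom model only, not the AK-reduction endpoint.

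**Working it through.** **Inputs.** From the documents: 10 per arm, two-sided alpha 0.05, power 0.80 and a 1.25-point difference (15.6); eligible counts 4 to 20 (6.2). Not in the documents, so assumed: the SD of pain (back-solved), the correlation rho between AK count and the symptom score (0 to 0.5), and a uniform count on the integers 4 to 20.

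**1. The plan's own figure.** Without an SD it cannot be reproduced, only inverted. For a two-sample t-test with 18 df and noncentrality d/√(2/10), power 0.80 requires d = 1.325. The implied SD is 1.25/1.325 = 0.943. The normal approximation gives 1.25/(√0.2 × (1.960 + 0.842)) = 0.998. The power comparisons in steps 2 to 4 are all made at d = 1.325.

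**2. Power after adjustment.** The covariate multiplies the residual variance by (1 − rho²). Chance differences in mean count inflate the variance by an expected 1 + 1/16 with two arms (17 error df) or 1 + 1/25 with three arms (26 error df). The noncentrality is

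d / √(0.2 × (1 − rho²) × inflation).

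For three arms at rho 0 it is 1.325/√(0.2 × 1.04) = 2.905, against 1.325/√0.2 = 2.963 for the t-test. At rho 0.5 it is 2.905/√0.75 = 3.355.

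| rho | Planned pairwise t-test | Two-arm model with count | Three-arm model with count |
|---|---|---|---|
| 0 | 0.800 | 0.773 | 0.799 |
| 0.3 | 0.800 | 0.810 | 0.834 |
| 0.4 | 0.800 | 0.840 | 0.862 |
| 0.5 | 0.800 | 0.878 | 0.898 |

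Simulation of the three-arm model (normal outcomes, equal variances, equal slopes) gives about 80%, 84%, 86% and 90% at these values of rho. Its type I error is 0.051 at rho 0.4.

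**3. What the covariate costs.** Pooling three arms with no covariate (27 df) already gives 0.815. At rho 0 the covariate therefore costs 0.815 − 0.799, about 1.5 points. In a two-arm fit it costs 0.800 − 0.773, or 2 to 3 points, and the detectable difference rises from 1.25 to 1.29. On variance, the two-arm model breaks even at rho = √(1 − 1/1.0625) = 0.24. The three-arm model, against three arms without the covariate, breaks even at √(1 − 1/1.04) = 0.20.

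**4. Unequal slopes.** If the daylight arm has no slope, simulated power of the three-arm model is about 81 to 83%. In a two-arm fit with rho 0.5 in the conventional arm and 0 in daylight, power is 0.802 against 0.803 for the t-test, so nothing is gained.

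**5. Size of a chance imbalance.** The SD of a uniform count on 4 to 20 is √((17² − 1)/12) = 4.90. The SD of the difference between two arm means is √(2/10) × 4.90 = 2.19, so a gap of 3 or more lesions has probability about 17%. If the count SD is 3.5, the probability is 5.5%. Such a gap shifts mean pain by 3 × rho × 0.943/4.90, which is 0.17 points at rho 0.3 and 0.29 at rho 0.5. Significance needs an observed difference of about 2.101 × 0.943 × √0.2 = 0.89 points.

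**The case against.** The strongest reply is that nothing here is wrong. Under randomization the unadjusted t-test is valid, and its standard error already allows for chance imbalance in lesion load. That stands.

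It also stands that the needed correlation is not documented. A reader might infer from section 2 that more lesions must mean more pain, because dysplastic cells accumulate PpIX. That section contrasts ways of delivering light and does not relate pain to lesion number. Symptoms are 0-10 intensity ratings, not sums over lesions (9.1.8), and every subject receives one Kerastick (8.4.1). The same mechanism could imply a flatter slope in the daylight arm, which would shrink the gain as in step 4.

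Adjustment is free in data collection but not statistically. The three-arm model matches the planned test at rho 0 because pooling the error term offsets the lost degree of freedom, not because of the covariate. Pooling assumes equal variances, which is doubtful if daylight scores sit near zero.

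The unstated SD is the larger gap. At SD 2, power for 1.25 points is 0.262 unadjusted and only 0.315 with two-arm adjustment at rho 0.5.

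The plan's description of itself as small and descriptive carries less weight, because it names formal tests, an alpha and a power. Section 15 also leaves room for the change, since a detailed SAP is still to be written.

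**Conclusion.** The point holds as a modest efficiency improvement. Measured against the planned pairwise t-test at its 80% point, the three-arm model loses essentially nothing at rho 0 and gains about 4, 6 and 10 points at rho 0.3, 0.4 and 0.5 with equal slopes, or 1 to 3 points if the daylight arm has no slope. About 1.5 points of any advantage come from pooling the arms rather than from the count. All of this rests on an assumed rho, common variance and uniform counts.

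Three stronger readings are not supported. The t-test is not biased. The five-fold span (20/4) is the eligibility range, not an observed spread. An imbalance of 3 lesions would not by itself create a significant tolerability difference, because a shift of about 0.2 to 0.3 points, at the back-solved SD of 0.94, is well short of the 0.89 needed.

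**What to change.** In section 15.3, the synopsis and the repeat in section 15.4, and in the SAP still to be written, prespecify one linear model across all three arms for each primary symptom endpoint: endpoint = arm (A, B, C) + Day 1 pre-ALA AK count. Report the adjusted A v C and A v B differences with 95% confidence intervals. Keep the unadjusted unpaired t-tests as a sensitivity analysis, because the model assumes a common slope and equal variances. Add the Day 1 AK count by arm to the baseline summaries in section 15.2, so that any imbalance is visible.

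The cost is wording only, with no added data or visits. Statistically it is one degree of freedom, as sized in step 3. Fit all three arms together rather than in pairs, since the pairwise version falls below the planned test when rho is under about 0.25. This change does not replace stating the SD behind section 15.6.

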8 STUDY TREATMENTS

8.1 Method of Assigning Subjects to Treatment Groups

Thirty eligible patients will be randomly assigned to one of three treatment arms (Conventional Arm, Combination Arm, Daylight Arm) in a 1:1:1 ratio using a SAS-based computer-generated randomization scheme developed by the study data management provider. The investigator or designee will complete a randomization worksheet prior to Visit 1.

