10.2 Visit 2 (Day 1, may be combined with Screening)

Unblinded investigator:

1. Randomization to treatment arms (1:1:1). Investigator will use sequential envelopes with randomly prefilled treatment arms. Envelopes will be filled in batches of three (nine patients) to ensure even allocation between arms during the course of treatment.
2. Perform and record vital signs.
3. Concomitant medications and Adverse Events review.

Blinded investigator:

4. Perform abbreviated physical examination.
5. Perform an AK count
6. Perform a pre-treatment local skin response assessment
7. Curette any hypertrophic AK
8. Application of ALA

Unblinded investigator:

9. Monitor ALA incubation duration depending on treatment arm
10. Light exposure (BLU-U and/or sunlight, depending on treatment arm)
11. Symptom assessment. All subjects will have symptom assessments at 15, 30, 45, 60, and 75 minutes (Table 2).
12. Skindex-16
13. Record any Adverse Events.
14. Photography of treatment area.

Blinded investigator:

15. Perform a post-treatment local skin response assessment

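### Patients are randomised in batches of nine, but the planned unpaired t-tests leave batch out, so any batch variation shared by the arms widens the confidence intervals and makes the tests conservative

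*Combined protocol and SAP*

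**What the plan says.** Section 4.1 sets the size: "Thirty adult subjects are planned; with 10 subjects in each of three treatment arms". Section 8.1 allocates "in a 1:1:1 ratio using a SAS-based computer-generated randomization scheme", and section 10.2 adds the restriction: "Envelopes will be filled in batches of three (nine patients) to ensure even allocation between arms during the course of treatment". The synopsis gives the time span: "Approximately 12 months for subject enrollment and 4 months for treatment and final subject follow-up".

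The analysis does not mention the batches. Section 15.3 compares peak symptom level and end-of-exposure pain between the conventional arm, "the combination treatment arm B), and the daylight treatment arm (C), with unpaired t-tests". Section 15.4 compares percent AK reduction between A and B, and "between the conventional treatment arm (A) and the daylight treatment arm (C), using unpaired t-tests". The synopsis repeats both. No section puts batch, calendar time or season into a comparison. Section 15 promises a separate SAP that may modify the plan, but describes no such adjustment.

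**The concern.** Filling envelopes in balanced batches is restricted randomisation over calendar time. Anything that moves outcomes in all arms together from one batch to the next (for example a change in how staff administer the symptom scales or apply the treatment) then falls equally on each arm and cancels from the difference in means. An unpaired t-test does not know this. It estimates error from the spread within each arm, and that spread still includes the differences between batches.

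At stake is precision. With ten patients per arm and no replacement of withdrawals, the reported intervals could be wider, and the tests weaker, than the design warrants.

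**Working it through.** **Inputs from the documents.** n = 10 per arm; batches of nine; 1.25 points of pain, two-sided alpha 0.05 and power 0.8 (section 15.6).

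**Assumptions.** Three patients per arm in each full batch. Thirty is not a multiple of nine, and the documents do not describe the last partial batch; it is taken as one per arm, giving per-arm batches of 3, 3, 3 and 1. The batch share of total variance, ρ, is not given and is varied.

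**The plan's own power figure.** No SD is stated, so solve for the one implied.
- Normal approximation: 1.25 / [(1.960 + 0.842) × √(2/10)] = 0.998.
- Exact two-sample t, 18 df: SD = 0.943, so d = 1.25 / 0.943 = 1.325.

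The stated power can be matched only through this back-solved SD. With SD 1.0, t-test power would be 0.753. The comparison below uses d = 1.325.

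**Why the estimated standard error is too large.** With balanced batches and a batch effect common to the arms:
- True variance of the difference in means: 2σ²(1 − ρ)/n.
- Expected within-arm variance used by the t-test: σ²(1 − ρ) + kρσ², where k = (10 − (9+9+9+1)/10)/9 = 7.2/9 = 0.8. This equals σ²(1 − 0.2ρ).
- Ratio of estimated to true standard error: √[(1 − 0.2ρ)/(1 − ρ)]. At ρ = 0.1, √(0.98/0.90) = 1.04; at 0.2, √(0.96/0.80) = 1.10; at 0.3, √(0.94/0.70) = 1.16.

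The true standard error itself falls without any batch term, from √0.2 = 0.447σ at ρ = 0 to √(0.2 × 0.7) = 0.374σ at ρ = 0.3.

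**Error degrees of freedom.** t-test 20 − 2 = 18; two-arm model with batch 20 − 4 − 1 = 15; three-arm model with batch 30 − 4 − 2 = 24.

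**Simulation, A v C, 100,000 trials per setting.**

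| ρ | Power: t-test | Power: two-arm batch model | Power: three-arm batch model | True size of t-test |
|---|---|---|---|---|
| 0 | 80.1% | 79.2% | 81.2% | 5% (by theory) |
| 0.05 | 80.9% | 81.0% | 83.1% | 4.5% |
| 0.10 | 81.6% | 83.1% | 84.9% | 4.1% |
| 0.20 | 83.5% | 87.2% | 88.8% | 3.5% |
| 0.30 | 85.0% | 90.9% | 92.3% | 2.9% |

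Both batch models hold about 5% size throughout. Independent repeat runs differ by about 0.1 point in size (4.0%, 3.6% and 2.8% at the last three shares). The two-arm model breaks even at about ρ = 0.05.

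**What drift each share implies.** Take σ = 0.943 (σ² = 0.890) and a steady drift common to all arms.
- Equal steps between batches with weights 0.3, 0.3, 0.3 and 0.1 have variance 0.96 × step², so the total drift is 3√(0.890ρ/0.96).
- Under a continuous trend, the batch means lie at 0.15, 0.45, 0.75 and 0.95 of enrolment, with variance 0.0765 × drift², so the drift is √(0.890ρ/0.0765).

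These give 0.65 to 0.76 points at ρ = 0.05, 0.9 to 1.1 at 0.10, 1.3 to 1.5 at 0.20 and 1.6 to 1.9 at 0.30.

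**Variation not shared by the arms.** If season moves only the daylight-exposed arms, a two-arm batch model at ρ = 0.2 gives 82% against 82% for the t-test.

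**The case against.** The strongest reply is that the balance already does its work. A reader might infer that batching helps only if batch is modelled, or that the plan gets nothing from it. That is wrong: the t-test's own power rises from 80% to 85% as ρ goes from 0 to 0.3, and the comparison stays protected against confounding with time, which is the purpose section 10.2 states. Only the estimated standard error fails to reflect the gain.

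Second, the mechanism has thin support for the primary endpoint. The one time-varying factor the protocol names is daylight: section 2 says "the effective light dose from natural daylight depends on geographic location and seasonal and weather changes". That acts on arms B and C, not on A. It is an arm-by-time difference that a common batch term does not remove. The trial has one site, and symptoms are patient-reported, although staff administer the scales. No passage points to drift common to all arms.

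Third, the larger gains need large drift. At a share of 20% or more, pain in every arm would have to move by at least as much as the 1.25-point effect the trial is sized for. This objection stands, and the lower rows of the table are the realistic ones.

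Finally, the study calls itself small and descriptive, and a fuller SAP is to follow. Yet the plan specifies tests and claims 80% power, interval width matters in descriptive work too, and the promised SAP is the natural place for the change.

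**Conclusion.** The point holds as an optional improvement in efficiency. The analysis omits the groups by which the trial randomises. If outcomes vary between batches in a way shared by the arms, the t-test's intervals are too wide and its tests conservative. At a 10% share the loss is about 1 to 3 points of power (two-arm or three-arm comparator), with true size near 4%. At 30% it is about 6 to 7 points, with size near 3%, but that needs an implausibly large drift. At zero nothing is lost.

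These sizes rest on an assumed ρ, on d = 1.325 back-solved from the stated power, and on the assumed 3, 3, 3, 1 split. A reader might infer that the t-tests are biased or reject too often. For variation shared by the arms neither follows: the estimate is unbiased and the error is on the cautious side. Nor should the point be read as a remedy for seasonal variation in daylight dose, which is a separate question.

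**What to change.** In section 15.3, and for percent AK reduction in section 15.4, pre-specify one linear model across all three arms with arm and randomisation batch (or the block finally used) as fixed terms. Report the A−C and A−B differences with 95% confidence intervals from it, and keep the unpaired t-test as a sensitivity analysis. State how the last partial batch is formed, and keep the envelope sequence number in the dataset so that batch can be derived.

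The cost is SAP wording. The three-arm model has 24 error degrees of freedom and loses nothing even at a batch share of zero (81% v 80%), but it relies on a common variance across arms. If that is thought doubtful, pairwise models with batch avoid pooling the third arm. They cost 3 error degrees of freedom (18 to 15), about 1 point of power when batch explains nothing.
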